8.1.4 Efficacy Measures and Analysis

Clinical endpoints

The primary efficacy measure will be the mean percent change from baseline to Visit 4/Day 84/Week 12 in the inflammatory (papules and pustules) lesion counts AND the mean percent change from baseline to Visit 4/Day 84/Week 12 in the non-inflammatory (open and closed) lesion counts. The secondary efficacy measure will be the proportion of subjects with clinical success on the Investigator's Global Assessment (IGA) at Visit 4/Day 84/Week 12. Success is defined as an IGA score that is at least 2 grades less than the baseline assessment.

Equivalent efficacy

For the mean percent reduction from baseline in the inflammatory and non-inflammatory lesion counts, the Test treatment will be considered to be therapeutically equivalent to the Reference treatment if the 90% confidence interval on the Test-to-Reference ratio of means, calculated by Fieller's Method, falls within the interval 0.80 to 1.25. The treatment means and estimate of residual variance for the confidence interval calculation will come from an Analysis of Variance of the Test and Reference results using a statistical model containing terms for Treatment and Site.

For the proportion of subjects with clinical success, the Test treatment will be considered to be therapeutically equivalent to the Reference treatment if the 90% confidence interval on the difference between Test and the Reference proportions is contained within the interval -20% to +20%. The confidence interval will be constructed using Wald's method with Yates' continuity correction.

Superiority

For the percent reductions from baseline in the inflammatory and non-inflammatory lesion counts, each active treatment will be evaluated to determine if it has superior efficacy to that of the Vehicle at Visit 4/Week 12/Day 84 via an Analysis of Variance using a statistical model containing terms for Treatment and Site.

The proportion of subjects with clinical success for each active treatment will be compared to that of the Vehicle using a Z-test with Yates' continuity correction.

All hypothesis tests will be two-sided at a significance level of $\alpha = 0.05$, except confidence intervals which will be based on $\alpha = 0.1$ (e.g., 90% coverage).

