5.5 Efficacy Variables and Analyses

5.5.1 Primary Endpoint

The two primary efficacy endpoints are the mean percent change from baseline to Visit 4/Week 12/Day 84 in the inflammatory (papules and pustules) lesion counts AND the mean percent change from baseline to Visit 4/Week 12/Day 84 in the non-inflammatory (open and closed) lesion counts.

Equivalent Efficacy

For the mean percent change from baseline in the inflammatory lesion counts, the Test treatment will be considered to be therapeutically equivalent to the Reference treatment if the 90% confidence interval on the Test-to-Reference ratio of means, calculated by Fieller's Method, falls within the interval 0.80 to 1.25. The compound hypothesis to be tested for therapeutic equivalence between test and reference is:

$$H_0: \mu_T / \mu_R \leq 0.80 \text{ or } \mu_T / \mu_R \geq 1.25 \text{ versus}$$

$$H_A: 0.80 < \mu_T / \mu_R < 1.25.$$

Where μ_T and μ_R are the mean percent change from baseline to Visit 4/Week 12/Day 84 in inflammatory lesions counts for the test treatment and the reference treatments, respectively.

The null hypothesis is rejected when the two-sided 90% confidence interval (CI) for the ratio of means between test and reference products is between 0.80 and 1.25. Rejection of the null hypothesis supports the conclusion of therapeutic equivalence between test and reference products for the primary efficacy variable.

The two-sided 90% confidence interval will be constructed using an ANOVA model with treatment and site as factors. [REDACTED]

The same analysis will be applied to the mean percent change from baseline in the non-inflammatory lesion counts.

[REDACTED]

Analysis for therapeutic equivalence will be performed based on the following SAS code (SAS Institute v.9.4), e.g. trt=1 for Test and trt=2 for Reference:

[REDACTED]

Where the ESTIMATE statement is run targeting at two-sided $p=0.10$ to locate the c value (our Test/RLD) for the 90% CI.

Superiority

For the mean percent change from baseline in the inflammatory lesion counts, each active treatment will be evaluated to determine if it has superior efficacy to that of the Vehicle at Visit 4/Week 12/Day 84 via an ANOVA model containing terms for treatment and site. The compound hypothesis to be tested for superiority of test and reference over Vehicle is:

$$H_0 : \mu_T \leq \mu_V \text{ or } \mu_R \leq \mu_V \text{ versus}$$

$$H_A : \mu_T > \mu_V \text{ and } \mu_R > \mu_V$$

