Where μ_T , μ_R and μ_V are the mean percent change from baseline to Visit 4/Week 12/Day 84 in inflammatory lesions counts for the test, the reference and the vehicle treatments, respectively. The null hypothesis is rejected when both p -values from the ANOVA are less than 0.05 (two-sided test). Rejection of the null hypothesis supports the conclusion of superiority of test and reference products over the vehicle product for the primary efficacy variable.

[REDACTED]

The same analysis will be applied to the mean percent change from baseline in the non-inflammatory lesion counts.

[REDACTED]

Analysis for superiority will be performed based on the following SAS code (SAS Institute v.9.4), e.g. trt=2 for Reference vs. trt=3 for Placebo:

[REDACTED]

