5.5.2 Secondary Endpoints

The secondary efficacy endpoint is the proportion of subjects with clinical success on the Investigator's Global Assessment (IGA) at Visit 4/Week 12/Day 84. Clinical success is defined as an IGA score that is at least 2 grades less than the baseline assessment.

Equivalent Efficacy

The compound hypothesis to be tested for clinical equivalence between test and reference is:

$$H_0: p_T - p_R < -0.20 \text{ or } p_T - p_R > 0.20 \text{ versus}$$

$$H_A: -0.20 \leq p_T - p_R \leq 0.20.$$

Where p_T and p_R are the proportions of subjects with clinical success at Visit 4/Week 12/Day 84 for the test and reference products, respectively. The test product will be considered to be therapeutically equivalent to the reference product if the 90% CI on the difference in their proportions of subjects with clinical success, calculated by Wald's method with Yates' continuity correction, is contained within the limits -0.20 to +0.20. Rejection of the null hypothesis supports the conclusion of therapeutic equivalence between the test and reference products for the secondary efficacy variable.

[REDACTED]

Analysis for therapeutic equivalence (i.e. 90% confidence interval) will be performed based on the following SAS code (SAS Institute v.9.4) e.g. trt=1 for Test and trt=2 for Reference:

[Redacted]

Superiority

The hypotheses to be tested for superiority of the test and reference products over Vehicle are:

$$H_0: p_T \leq p_V \text{ versus } H_A: p_T > p_V$$

$$H_0: p_R \leq p_V \text{ versus } H_A: p_R > p_V$$

Where p_T , p_R and p_V are the proportions of subjects with clinical success at Visit 4/Week 12/Day 84 for the test, reference and Vehicle products, respectively. The tests will be conducted independently for the test product vs. vehicle and the reference product vs. vehicle using two-sided, $\alpha = 0.05$, continuity-corrected Z-tests. Superiority will be established if the proportion of subjects with clinical success in the active treatment group is greater than and statistically different ($p < 0.05$) from that in the Vehicle. Rejection of the null hypothesis supports the conclusion of superiority of the test and reference products over the Vehicle product for the secondary efficacy variable.

[Redacted]

Analysis for superiority (continuity-corrected p-value for treatment comparison) will be performed based on the following SAS code (SAS Institute v.9.4) e.g. trt=2 for Reference vs. trt=3 for Placebo:

[Redacted]

5.5.3

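### Does the primary superiority rule in SAP 5.5.1 lack a direction, or point the wrong way, because it is written for percent change?

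*SAP*

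**What the plan says.** SAP 5.5.1, under Superiority, opens with the aim: "each active treatment will be evaluated to determine if it has superior efficacy to that of the Vehicle". It then prints a compound null, μ_T ≤ μ_V or μ_R ≤ μ_V, against the alternative μ_T > μ_V and μ_R > μ_V. The means are defined as the "mean percent change from baseline to Visit 4/Week 12/Day 84 in inflammatory lesions counts for the test, the reference and the vehicle treatments". The null is rejected when both p-values "from the ANOVA are less than 0.05 (two-sided test"), and rejection "supports the conclusion of superiority of test and reference products over the vehicle product". The same analysis is applied to non-inflammatory lesions. Text after the rule is redacted, and so is the SAS code.

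Protocol 8.1.4 uses both terms for this measure. It names the endpoint as change ("The primary efficacy measure will be the mean percent change from baseline") but frames the superiority analysis as reduction ("For the percent reductions from baseline in the inflammatory and non-inflammatory lesion counts, each active treatment will be evaluated"). It also frames the equivalence analysis as reduction.

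For the secondary IGA endpoint, SAP 5.5.2 puts the direction into the decision sentence itself: "Superiority will be established if the proportion of subjects with clinical success in the active treatment group is greater than and statistically different" from vehicle at the 0.05 level.

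**The concern.** An effective acne treatment lowers lesion counts. If percent change is follow-up minus baseline, divided by baseline, a good result is a negative number, and an alternative with each active mean above the vehicle mean describes actives that work less well than vehicle. The decision sentence does not repair this, because a two-sided p-value below 0.05 does not say which arm is better. SAP 5.5.2 does state the direction, so its absence in 5.5.1 stands out.

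Superiority of both actives over vehicle is a stated objective, and this sentence is its decision rule on the primary endpoints. Two literal misreadings are possible. Someone who looks only at the p-values could accept a result that favours vehicle. Someone who programs the printed inequality on follow-up-minus-baseline change would record a real success as a failure.

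**Working it through.** **No figure to reproduce.** The sample size, assumed effect, standard deviation and allocation ratio are redacted (Protocol 8.1.3, SAP 3.2, Protocol 6.2.4). The arm sizes, means and SD below are assumptions. The 0.05 two-sided level and the 0.80 to 1.25 limits come from SAP 5.5.1.

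**1. What the sign affects.** Take illustrative changes of −60 (Test), −58 (Reference) and −40 (vehicle).
- As change, −60 > −40 is false, although Test is better. As reduction, 60 > 40 is true. The printed inequality therefore fits the reduction scale.
- Reversing the sign of the analysis variable reverses the t statistic and leaves its two-sided p-value unchanged.
- The equivalence ratio is −60/−58 = 60/58 = 1.034 either way.

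**2. How often p-values alone would favour vehicle if nothing works.** The two active-versus-vehicle statistics share the vehicle arm, so their correlation is r = 1/(1 + n_V/n_A). With critical value 1.96 and three truly equal arms, the bivariate normal gives the chance that both statistics fall below −1.96:

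| Allocation | r | Both favour vehicle | Both favour actives |
|---|---|---|---|
| 1:1:1 | 0.500 | 0.46% | 0.46% |
| 2:2:1 | 0.667 | 0.75% | 0.75% |
| 3:3:1 | 0.750 | 0.95% | 0.95% |

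The chance of significance in opposite directions is below 0.001%.

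**3. The same, also requiring equivalence.** A successful trial also needs the 90% Fieller interval that "falls within the interval 0.80 to 1.25". Simulating with SD 40 and a true mean reduction of 40 to 60 in every arm, the vehicle-favouring case remains at 0.27% to 0.45% (200:200:200), 0.72% to 0.75% (400:400:200) and 0.82% to 0.96% (300:300:100). The equivalence criterion does not remove it, but it stays below 1%.

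**4. If the actives work.** With both actives two standard errors better than vehicle, the chance that both tests are significant in vehicle's favour is 6.1 × 10⁻⁷, 2.3 × 10⁻⁶ and 4.3 × 10⁻⁶ for 1:1:1, 2:2:1 and 3:3:1.

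**5. Power with and without a stated direction.** Take reductions of 55 in both actives and 40 in vehicle, with SD 40. The standard error of each difference is 40 × √(1/n_A + 1/n_V):

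| Arms | SE | 15/SE | Both p < 0.05, no direction | Same, direction required |
|---|---|---|---|---|
| 200:200:200 | 4.00 | 3.75 | 93.5% | 93.5% |
| 400:400:200 | 3.46 | 4.33 | 98.5% | 98.5% |
| 300:300:100 | 4.62 | 3.25 | 85.3% | 85.3% |

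**6. Mixed directions.** Suppose the reductions are 20 (Test), 55 (Reference) and 30 (vehicle), so that Test is worse than vehicle. Both p-values would be below 0.05 in 70.6%, 82.3% and 58.1% of trials for the three sets of arm sizes, almost always in opposite directions. No simulated trial also met the equivalence criterion.

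**The case for a change.** The strongest case for a change is that the SAP governs the analysis: Protocol section 8 makes it the reference document for the statistical evaluation. A primary decision rule should not rely on the reader to supply the sign. No visible text defines it, Protocol 8.1.4 uses both terms, and the SAP already has better wording in 5.5.2. Two sentences before unblinding would cost nothing.

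Part of this stands. The visible text of 5.5.1 says change where reduction would be clearer, and its decision sentence is less explicit than the one in 5.5.2.

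The rest does not carry. The decision sentence is about rejecting the null printed just above it, and that null has a direction; calling the rule directionless means setting the hypotheses aside. The backwards reading needs a follow-up-minus-baseline convention that no visible text adopts, while the protocol treats improvement as positive in both the equivalence and the superiority analysis. The outcome in which a success is recorded as a failure needs a one-directional test on the negative scale, whereas the SAP specifies two-sided ANOVA p-values. Finally, text is blacked out directly after the rule and where the code stood. The sign may be defined there, and redacted text cannot be counted as missing.

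**Conclusion.** The wording is loose, but the test it describes is clear: two-sided p below 0.05 for each active against vehicle, with the active showing the larger reduction. An analyst reading the SAP beside Protocol 8.1.4 would apply exactly that. The choice of sign changes neither the p-values nor the equivalence ratio, and stating the direction changes power by nothing in the cases examined.

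The only measurable exposure is a result favouring vehicle being called superiority. It is 0.46% to 0.95% per endpoint if all three arms are truly identical, and no larger at trial level if both lesion types must succeed. It is at most 4.3 × 10⁻⁶ once the actives lead by two standard errors. These figures assume normal statistics and allocations from 1:1:1 to 3:3:1; those that include equivalence or power also assume an SD of 40 and the arm sizes shown. Even then, someone would have to report as superior a product that did significantly worse than vehicle, against the stated hypotheses. This is a matter of terminology, and no change to the plan is called for.

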5.5.2 Secondary Endpoints

The secondary efficacy endpoint is the proportion of subjects with clinical success on the Investigator's Global Assessment (IGA) at Visit 4/Week 12/Day 84. Clinical success is defined as an IGA score that is at least 2 grades less than the baseline assessment.

Equivalent Efficacy

The compound hypothesis to be tested for clinical equivalence between test and reference is:

$$H_0: p_T - p_R < -0.20 \text{ or } p_T - p_R > 0.20 \text{ versus}$$

$$H_A: -0.20 \leq p_T - p_R \leq 0.20.$$

Where p_T and p_R are the proportions of subjects with clinical success at Visit 4/Week 12/Day 84 for the test and reference products, respectively. The test product will be considered to be therapeutically equivalent to the reference product if the 90% CI on the difference in their proportions of subjects with clinical success, calculated by Wald's method with Yates' continuity correction, is contained within the limits -0.20 to +0.20. Rejection of the null hypothesis supports the conclusion of therapeutic equivalence between the test and reference products for the secondary efficacy variable.

[REDACTED]

Analysis for therapeutic equivalence (i.e. 90% confidence interval) will be performed based on the following SAS code (SAS Institute v.9.4) e.g. trt=1 for Test and trt=2 for Reference:

[Redacted]

Superiority

The hypotheses to be tested for superiority of the test and reference products over Vehicle are:

$$H_0: p_T \leq p_V \text{ versus } H_A: p_T > p_V$$

$$H_0: p_R \leq p_V \text{ versus } H_A: p_R > p_V$$

Where p_T , p_R and p_V are the proportions of subjects with clinical success at Visit 4/Week 12/Day 84 for the test, reference and Vehicle products, respectively. The tests will be conducted independently for the test product vs. vehicle and the reference product vs. vehicle using two-sided, $\alpha = 0.05$, continuity-corrected Z-tests. Superiority will be established if the proportion of subjects with clinical success in the active treatment group is greater than and statistically different ($p < 0.05$) from that in the Vehicle. Rejection of the null hypothesis supports the conclusion of superiority of the test and reference products over the Vehicle product for the secondary efficacy variable.

[Redacted]

Analysis for superiority (continuity-corrected p-value for treatment comparison) will be performed based on the following SAS code (SAS Institute v.9.4) e.g. trt=2 for Reference vs. trt=3 for Placebo:

[Redacted]

5.5.3

[Redacted]

[Redacted]

5.6 Safety Variables and Analyses

Duration of Treatment and Medication Compliance

Number of applications, days of exposure (i.e. duration of treatment), and compliance rate will be summarized by treatment group using descriptive statistics. For each subject, the duration of treatment (days) will be calculated using the following formula:

$(\text{Date of last application of study medication}) - (\text{Date of first application of study medication}) + 1.$

Medication compliance rate (%) will be calculated for each subject as follows:

$(\text{Total number of applications used}) / (\text{Expected number of applications}) * 100\%.$

[REDACTED] For prematurely discontinued subjects, expected number of applications will be determined based on the expected number of applications by the time of discontinuation, i.e. overall duration of treatment. Descriptive summaries of exposure and medication compliance rate will be provided by treatment group for the ITT subjects.

Adverse Events

Adverse events (AEs) will be coded in MedDRA, version 20.0. Treatment-Emergent Adverse Event (TEAE) is defined as any AE occurs on or after application of the first dose of study drug. Number and percent of subjects reporting TEAEs will be tabulated by treatment group. Summaries will be presented by body system and preferred term for the ITT population, and further by severity and relationship to study medication. TEAEs reported by 5% or more subjects for any treatment group will be summarized by preferred term. In the summaries of incidence rates (frequencies and percentages), severity and relationship to study drug, subjects who report more than one event that are mapped to the same preferred term will be counted only once under the strongest severity and relationship, accordingly. The difference between Test and Reference treatments with regard to severity and frequency of their dermatological adverse events will be statistically evaluated using Chi-Square or Fisher's exact test to compare the proportions of subjects of the two active treatment groups who report any TEAE.

Treatment-Emergent Serious Adverse Events (TESAEs) will be discussed within the clinical study report. TEAEs, TESAEs and TEAEs that led to treatment interruption or discontinuation will be presented in data listings.

Concomitant Medications and Vitals Signs

Concomitant medications will be coded using the WHO Drug Dictionary, version March 2017, and will be presented in data listings. All vital signs data will be displayed in listings.

Application Site Reaction Assessments

Frequency and distribution of application site reactions of erythema, dryness, scaling/peeling, burning/stinging, erosion, edema, pain and itching will be summarized and compared descriptively by visit.

Safety comparisons will be performed only for the ITT population.

6 Appendices

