5.16 Subject/Treatment Compliance

[REDACTED] the study medication onto each area of the face (forehead, chin, right cheek, left cheek, and nose) [REDACTED] and avoiding contact with the eyes, lips, inside your nose/nostrils, angles of the nose, broken skin and mucous membranes at approximately the same time once daily [REDACTED] for 12 weeks. [REDACTED]

On Day 1, subjects will apply their initial dose of study medication at the study site under the supervision of the third-party dispenser staff or other designee. Compliance will be determined from the diary card, in which the subject will be instructed to record all applications made or

[REDACTED]

missed. On Week 2 Day 14/ (± 4 days), compliance will be assessed via telephone contact. The study coordinator, or designee, will review the Subject Instruction Sheet and Diary with the subject on the phone. The total number of study medication doses applied and/or missed will be determined based upon the first dose applied through and including the last dose applied. The first and last dates of treatment should be recorded in the source documents and eCRFs. The total of applied and missed study medication applications should also be recorded. By definition there are no missed applications before the first date of treatment or after the last date of treatment.

[REDACTED]

All used and unused pump bottles of study medication will be collected by the study site at appropriate visits or early termination.

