5.17 Discontinuation/Withdrawal of Study Subjects

Subjects may be removed from the study for any of the following reasons:

- The subject withdraws his or her consent for any reason.
- The subject's condition has worsened to the degree that the investigator feels it is unsafe for the subject to continue in the study or requires an alternative therapy.
- The subject's medication code is unblinded.
- Subject did not meet or no longer meets the entry criteria.
- An adverse event including intercurrent illness, occurs for which the subject desires to discontinue treatment or the investigator determines that it is in the subject's best interest to be discontinued.
- The subject is lost to follow-up. The investigator will document efforts to attempt to reach the subject twice by telephone and will send a certified follow-up letter before considering that subject lost to follow-up. All attempts must be thoroughly recorded.
- The subject becomes pregnant during the course of the trial.
- [REDACTED]
- Investigator discretion (e.g., non-compliant to study protocol requirements).

After a subject has been discontinued, he/she will not be allowed to re-enroll in the study at any facility.

The reasons for a subject being discontinued will be documented in the eCRFs and the enrollment log.

If a subject is discontinued from the study for any reason, the Visit 4 (Day 84)/End of Study Visit/Early Termination Visit procedures should be completed and any outstanding data and study medication should be collected. Data, in addition to the reason for discontinuation and the date of removal, will be recorded on the Source Document and End of Study eCRF.

In the event that a subject discontinues from the study at any time due to an adverse event, the reason for discontinuation, the nature of the event and its clinical course must be fully

[REDACTED]

documented. For such a subject, the investigator must strive to follow the subject until the adverse event has resolved, become clinically insignificant, is stabilized, or the subject is lost to follow-up.

[REDACTED]

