8.1 Statistical Analysis Plan

8.1.1 Analysis Populations

The following populations are defined for the purpose of analyses:

- Intent-to-Treat (ITT) (safety population): Any subject that was randomized, received and used study medication.

- Modified Intent-to-Treat (mITT): Any subject, who met the inclusion/exclusion criteria, was randomized, received and used the study medication, and returned for at least one post-baseline efficacy assessment.

- Per Protocol (PP): Any subject who:
 - met inclusion/exclusion criteria,
 - was randomized, received and used study medication,
 - met the protocol criteria for compliance [REDACTED]
[REDACTED] and
 - completed Visit 4/Week 12/Day 84 (End of Treatment/Early Termination Visit) efficacy evaluations within the designated window (± 4 days) OR was discontinued from the study due to treatment failure and
 - had no significant protocol violations that could have interfered with the administration of the treatment or the precise evaluation of treatment efficacy.

[REDACTED]

[REDACTED]

[REDACTED]

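### Does ending the compliance denominator at the last dose overstate compliance for subjects who leave the trial early?

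*SAP*

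**What the plan says.** SAP 5.6 defines a subject's compliance rate as applications used divided by applications expected, times 100%. For early discontinuers, the "expected number of applications will be determined based on the expected number of applications by the time of discontinuation, i.e. overall duration of treatment". The same section computes duration of treatment as the "Date of last application of study medication" minus the date of the first, plus 1.

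Protocol 5.16 gives the counting rule behind this. The totals of applied and missed doses "will be determined based upon the first dose applied through and including the last dose applied", and "By definition there are no missed applications before the first date of treatment or after the last date of treatment". It also requires that "The first and last dates of treatment should be recorded in the source documents and eCRFs".

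Protocol 5.17 collects a further date for subjects who leave: "the reason for discontinuation and the date of removal, will be recorded on the Source Document and End of Study eCRF".

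On use, SAP 5.6 says "Descriptive summaries of exposure and medication compliance rate will be provided by treatment group for the ITT subjects". Separately, the per-protocol (PP) definition in Protocol 8.1.1 requires that a subject "met the protocol criteria for compliance"; the detail of that criterion is redacted.

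**The concern.** The SAP sentence joins two things that need not coincide: the time of discontinuation and the length of treatment. The protocol records the last treatment date and the removal date separately, and they differ whenever a subject stops applying the gel some time before leaving. The sentence then takes the shorter period, so a subject who quietly stops and is removed weeks later can be tabulated as fully compliant.

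Two things would be at stake. The ITT compliance tables could look better than actual use over the study period. And because PP admits subjects discontinued for treatment failure if they meet the compliance criterion, a treatment failure who had stopped applying might enter the PP equivalence analysis.

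**Working it through.** **Inputs.** Dosing is once daily (SAP 3.1), so expected applications equal days in the window. The first dose is on Day 1 (Protocol 5.16). Let s be the day of the last dose, d the day of discontinuation, and m the doses missed before s. The plan states no compliance figure, so there is none to reproduce; the cases below are illustrations.

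**Formulas.**
- Rate as planned: (s − m) / s
- Rate over time on study: (s − m) / d

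| Last dose s | Discontinued d | Missed m | As planned | Over time on study |
|---|---|---|---|---|
| 20 | 20 | 0 | 20/20 = 100% | 20/20 = 100% |
| 20 | 40 | 0 | 20/20 = 100% | 20/40 = 50.0% |
| 42 | 56 | 0 | 42/42 = 100% | 42/56 = 75.0% |
| 56 | 60 | 6 | 50/56 = 89.3% | 50/60 = 83.3% |
| 35 | 56 | 1 | 34/35 = 97.1% | 34/56 = 60.7% |

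With no gap the rates are equal. Doses missed before the last dose count under both. Only days after the last dose separate them.

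**Effect on an arm mean.** If a fraction f of an arm discontinues on Day 56, fully compliant up to day s, the difference is f × (100 − 100 × s/56) percentage points.
- No gap (s = 56): 0 for any f
- f = 5%, s = 49: 0.05 × 12.5 = 0.6
- f = 10%, s = 42: 0.10 × 25 = 2.5
- f = 20%, s = 28: 0.20 × 50 = 10.0

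The values of f and s are assumptions. The upper end needs one fifth of an arm to stop at Day 28 yet stay on study to Day 56. Nothing in the documents points to a difference between arms.

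**Do the documents conflict?** Protocol 5.16 ends the count at the last dose. The SAP's treatment duration also ends at the last dose. Read as stopping medication, discontinuation in the SAP sentence is the same date, and the sentence agrees with itself and with the protocol. The removal date in Protocol 5.17 is a disposition item; neither document makes it the end of the compliance window.

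**Is early stopping hidden?** No. SAP 5.6 summarises number of applications and days of exposure by arm alongside the rate, and SAP 5.4 tabulates disposition and reasons for discontinuation by arm. A subject who stops on Day 20 appears with 20 days of exposure. The gap itself can be computed from dates already collected.

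**Can it alter PP?** Most early leavers fail PP because they have no in-window Visit 4. The exception is discontinuation for treatment failure (Protocol 8.1.1; SAP section 4). For the rate to matter there, such a subject must have stopped well before removal, the redacted criterion must use this rate, and the subject must not be excluded for a significant protocol violation. The visible text does not establish the second condition.

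**Would the other denominator be better?** It brings its own distortion. Protocol 4.4 lets the investigator stop treatment for irritation. A subject told to stop after the Day 21 dose and removed on Day 28 would score 21/28 = 75% despite following every instruction. If the missed-dose rule were also extended to all days before Week 12, a completer seen in window on Day 80 with a last dose on Day 79 would be charged for Days 80 to 83: 79/83 = 95.2% instead of 79/79 = 100%.

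**The case for a change.** The strongest argument needs no outside benchmark. A subject who applies daily to Day 42, stops, and is removed on Day 56 scores 42/42 = 100%. A subject identical except for one more dose on Day 56 scores 43/56 = 76.8%. Using more gel lowers the rate. Protocol 5.17 also allows removal for non-compliance, so someone removed for not applying the gel could be listed as fully compliant. Gaps are foreseeable too: clinic visits are four weeks apart, local irritation is expected, and loss to follow-up is declared only after two calls and a certified letter.

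The arithmetic stands, and so does the observation that the SAP wording could be read two ways. But the reversal follows from any rule that separates missing doses during treatment from having ended treatment: the first subject ended, the second interrupted and resumed. The planned tables tell them apart, with 42 days of exposure and 42 applications against 56 days and 43 applications. A rate over time on study avoids the reversal but counts instructed stopping as non-compliance. This is a choice between two measures, and the protocol made it openly and in advance.

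**Conclusion.** The concern does not hold. Protocol 5.16 and SAP 5.6 use the same first-to-last-dose window, and the resulting rate is a prespecified measure of compliance while on treatment. It is overstated only if one expects compliance over time on study.

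For a single subject the two measures can differ greatly (100% against 50% in the Day 20 and Day 40 example). For an arm mean the difference is 0 to 10 percentage points, resting entirely on assumed discontinuation rates and gaps. The visible use is descriptive, no hypothesis test uses the rate, and exposure and disposition are reported by arm as well. An effect on PP membership is conceivable only through a chain of conditions that depends on redacted text, and any effect on the equivalence ratio cannot be computed.

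This rests on reading discontinuation in the SAP sentence as the end of treatment, which its own gloss and Protocol 5.16 both support. Saying so explicitly would be an optional clarification. A change of denominator would be a trade-off, and by Protocol 10.2 a permanent change to the protocol rule must be handled as an amendment.
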